5.6 Concomitant Medications

Supportive care measures including blood products, infection prophylaxis and growth factors will be administered according to institutional and MDACC Leukemia Department guidelines (Table 11).

Table 11: Instructions for the use of concomitant medications and therapies

Category of Use	Medication	Comment on Use	Restriction on Use
Recommended	Prophylactic antibiotics, antifungal agents, and antiviral agents	Strongly encouraged	None
	Antiemetic agents	According to standard of care at MDACC	None
Allowed	Oral allopurinol or rasburicase	At investigators discretion	None
	Leukapheresis	According to standard of care at MDACC	Before induction 1 day 1 only

Category of Use	Medication	Comment on Use	Restriction on Use
	Red blood cell transfusion	None	None
	Platelet transfusion	None	None
	White blood cell transfusion	At investigators discretion according to standard of care at MDACC	None
	Myeloid growth factors or platelet growth factor	At investigators discretion according to standard of care at MDACC	None
	Erythropoietin or darbepoietin	At investigators discretion according to standard of care at MDACC	None
	Any other medication for supportive care	At investigators discretion according to standard of care at MDACC	None
	CYP3A4 inducers, inhibitors in patients on venetoclax or glasdegib, TdP drugs, QT prolonging drugs in patients on glasdegib	Please see section 5.5.6 and 5.4.7 for guidelines on use of these agents	

Consistent with subject safety and comfort, administration of any prescription or over-the-counter drug products other than study medication should be minimized during the study period. Subjects should be discouraged from use of street drugs, herbal remedies, self-prescribed drugs, tobacco products, or excessive alcohol during the clinical study.

If considered necessary for the subject's wellbeing, drugs for concomitant medical conditions or for symptom management may be given at the discretion of the

investigator. The investigator's decision to authorize the use of any drug other than study drug should take into account subject safety, the medical need, the potential for drug interactions, the possibility for masking symptoms of a more significant underlying event, and whether use of the drug will compromise the outcome or integrity of the study.

Subjects should be instructed about the importance of the need to inform the clinic staff of the use of any drugs or remedies (whether prescribed, over-the- counter, or illicit) before and during the course of the study.

Recommendations with regard to specific types of concomitant therapies, supportive care; diet and other interventions are as follows:

Concomitant medications are recommended as prophylaxis for nausea, vomiting, and infections, and are allowed for managing myelosuppression as shown in Table 3. Myelosuppression is expected in patients with AML due to underlying disease, as well as due to chemotherapy (such as azacitidine), or both. Most patients have neutropenia, thrombocytopenia, or both at study entry. Significant or life-threatening myelosuppression may be managed with growth factor support and blood transfusion according to institutional standard of care, American Society of Clinical Oncology (ASCO) Practice Guidelines, and/or NCCN Practice Guidelines.

Infections secondary to myelosuppression are common in patients with AML, and may be related to underlying disease, chemotherapy, or both. Therefore, the use of prophylactic antibiotics, antifungal agents, and antiviral agents is recommended according to institutional standards.

Since the effect of IO-agents, azacitidine, smoothed inhibition may be delayed, patients with high WBC counts may receive hydroxyurea prior to study entry. Hydroxyurea is allowed before the start of study therapy and during the study treatment. Hydroxyurea use would be recorded in the case report form (CRF). Concurrent therapy for CNS prophylaxis or continuation of therapy for controlled CNS disease is permitted. With the exception of these agents, concomitant systemic chemotherapy or radiation therapy is not permitted. Subjects are not allowed to participate concurrently in any other therapeutic clinical study to treat the underlying disease but are eligible to enroll on supportive care clinical trials.

Subjects may be receiving systemic corticosteroids (daily doses \leq 10 mg of prednisone or equivalent if indicated for adrenal replacement or antiemetic therapy), topical, or inhaled corticosteroids at study enrollment. They may receive systemic, topical, inhaled, or enteric corticosteroids while on study without limitation if they develop conditions that require corticosteroid therapy; such subjects are not required to discontinue study participation.

All ongoing medications and therapies (including herbal products, nutritional supplements, and nontraditional medications) at screening will be considered prior medications. Concomitant medication data will not be collected or entered into the case report form other than hydroxyurea as mentioned above; however, the subject's medication record will contain a list of concomitant medications. If a prohibited medication is inadvertently administered/ taken by the patient, the patient may remain on study as long as the prohibited medication is discontinued as soon as feasible. If a prohibited medication is considered essential for the patient well being, continuation on

study with concomitant administration of such medication(s) will need to be discussed with and approved by the principal investigator and medical monitor

6.0 DRUG ADMINISTRATION

6.1 IO-agent Patient Monitoring During Infusion (avelumab and PF-04518600)

Vitals should be checked prior to dosing, at least once during infusion, and at least once after completion of infusion.

6.2 Treatment of IO-agent/s Related Infusion Reactions

Since avelumab and PF-04518600 contains only human immunoglobulin protein sequences, they are unlikely to be immunogenic and induce infusion or hypersensitivity reactions. However, if such a reaction were to occur, it might manifest with fever, chills, rigors, headache, rash, pruritus, arthralgias, hypo- or hypertension, bronchospasm, or other symptoms. All Grade 3 or 4 infusion reactions should be reported within 5 days to the Pfizer Medical Monitor and reported as an SAE if criteria are met. Infusion reactions should be graded according to NCI CTCAE (version 4.03) guidelines.

Treatment recommendations for IO-agent related infusion reactions, including severe hypersensitivity reactions and tumor lysis syndrome (TLS) are provided below and may be modified based on MD Anderson treatment standards and guidelines, as appropriate:

A. IO-agent Infusion Related Reactions

Symptoms

- Fever
- Chills
- Rigors
- Diaphoresis
- Headache

Table 12. Treatment Modification for Symptoms of Infusion-Related Reactions

NCI-CTCAE Grade	Treatment Modification for Study Drug
Grade 1 – mild Mild transient reaction; infusion interruption not indicated; intervention not indicated.	Decrease the study drug infusion rate by 50% and monitor closely for any worsening. The total infusion time for study drug should not exceed 120 minutes.
Grade 2 – moderate Therapy or infusion interruption indicated but responds promptly to symptomatic treatment (for example, antihistamines, NSAIDs, narcotics, IV fluids); prophylactic medications indicated for ≤ 24 h.	Stop study drug infusion. Resume infusion at 50% of previous rate once infusion-related reaction has resolved or decreased to at least Grade 1 in severity, and monitor closely for any worsening.
Grade 3 or Grade 4 – severe or life-threatening Grade 3: Prolonged (for example, not rapidly responsive to symptomatic medication and/or brief interruption of infusion); recurrence of symptoms following initial improvement; hospitalization indicated for clinical sequelae. Grade 4: Life-threatening consequences; urgent intervention indicated.	Stop the study drug infusion immediately and disconnect infusion tubing from the subject. Subjects have to be withdrawn immediately from study drug treatment and must not receive any further study drug treatment.

 - Once the infusion rate has been decreased by 50% or interrupted due to an infusion-related reaction, it must remain decreased for all subsequent infusions. - If the subject has a second infusion-related reaction Grade ≥ 2 on the slower infusion rate, the infusion should be stopped and the subject should be removed from study treatment unless the patient is deriving clinical benefit in which the agent may be continued after discussion with the PI of potential risk/benefit ratio and documentation of this discussion in the patient's medical record. - If hypersensitivity reaction occurs, the subject must be treated according to the best available medical practice. 	

IV = intravenous; NCI-CTCAE = National Cancer Institute-Common Terminology Criteria for Adverse Event; NSAIDs = nonsteroidal anti-inflammatory drugs.

[figure not shown]
B. Severe Hypersensitivity Reactions and Flu-Like Symptoms

If hypersensitivity reaction occurs, the subject must be treated according to the best available medical practice. Subjects should be instructed to report any delayed reactions to the Investigator immediately.

C. Tumor Lysis Syndrome

In addition, since IO-agents can induce antibody-dependent cell-mediated cytotoxicity, there is a potential risk of tumor lysis syndrome. Should this occur, subjects should be treated per the local guidelines and the management algorithm below ([Howard 2011](#)).

Assessment and Initial Management of Tumor Lysis Syndrome

TLS = tumor lysis syndrome

6.3 Azacitidine:

Azacitidine will be commercially obtained. Refer to azacitidine prescribing information (Appendix) in addition to institutional standards for preparation and administration azacitidine.

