If the criteria to resume treatment are met, the subject should restart treatment at the next scheduled time point per protocol. However, if the treatment is delayed past the next scheduled time point per protocol, the next scheduled time point will be delayed until dosing resumes. Patients who receive combination therapy in whom continuation of the non-IO agent(s) (e.g. azacitidine, GO and/or venetoclax) is considered to be inadequate, or inappropriate (e.g., because of pancytopenia or other considered related severe toxicity) can discontinue these agents and continue with IO-agent only.

Patients who are experiencing ongoing dose delays > 8 weeks due to unresolved grade ≥ 3 adverse events should be taken off treatment, except as specified in discontinuation section.

5.4.4 IO-agent Discontinuation Criteria: The following clinically significant, drug-related ADRs require permanent treatment discontinuation of any IO=agent/s:

---Any Grade 4 drug-related AEs require treatment discontinuation with IO-agent/s except for single laboratory values out of normal range that are unlikely related to study treatment as assessed by the Investigator, do not have any clinical correlate, and resolve within 7 days with adequate medical management

---Any Grade 3 drug-related AEs require treatment discontinuation with IO-agent/s except for any of the following:

- Transient (\leq 6 hours) Grade 3 flu-like symptoms or fever, which is controlled with medical management
- Transient (\leq 24 hours) Grade 3 fatigue, local reactions, headache, nausea, emesis that resolves to Grade \leq 1
- Single laboratory values out of normal range (excluding Grade \geq 3 liver function test increase) that are unlikely related to study treatment according to the Investigator, do not have any clinical correlate, and resolve to Grade \leq 1 within 7 days with adequate medical management
- Tumor flare phenomenon defined as local pain, irritation, or rash localized at sites of known or suspected tumor
- Change in ECOG PS to \geq 3 that does not resolve to \leq 2 within 14 days (infusions should not be given on the following cycle, if the ECOG PS is \geq 3 on the day of study drug administration)

Any Grade 2 drug-related AEs should be managed as follows:

- If a Grade 2 AE resolves to Grade \leq 1 by the last day of the current cycle, treatment may continue.

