- If a Grade 2 AE does not resolve to Grade \leq 1 by the last day of the current cycle, infusions should not be given on the following cycle. If at the end of the following cycle the event has not resolved to Grade 1, the subject should permanently discontinue treatment with IO-agent/s (except for hormone insufficiencies, that can be managed by replacement therapy; for these hormone insufficiencies, up to 2 subsequent doses may be omitted).
- Upon the second occurrence of the same Grade 2 AE (except for hormone insufficiencies that can be managed by replacement therapy) in the same subject, treatment with the IO-agent/s has to be permanently discontinued unless the patient is deriving clinical benefit in which case the agent may be continued after discussion with the PI of potential risk/benefit ratio and documentation of this discussion in the patient's medical record.
- Infusion-related reactions, hypersensitivity reactions (Grades 1 to 4), and tumor lysis syndrome should be handled according to guidelines provided.
- Any dosing interruption due to drug-related toxicity lasting $>$ 8 weeks

5.4.5 Detailed management algorithms for immune-oncology drug-related adverse events (including gastrointestinal, renal, pulmonary, hepatic, endocrine, skin and neurological) are provided in Table 4 below. These general guidelines constitute guidance to the Investigator and may be supplemented by discussions with the PI and IND Office in specific cases.

Since IO-agent/s stimulates the immune system, immune-related AEs (irAEs) may occur. Treatment of irAEs is mainly dependent upon severity (NCI-CTCAE grade): Grade 1 to 2: treat symptomatically or with moderate dose steroids, more frequent

monitoring

Grade 1 to 2 (persistent): manage similar to high grade AE (Grade 3 to 4)

Grade 3 to 4: treat with high dose corticosteroids

Table 4. Management of Immune-Related Adverse Events (irAEs) (These are to be followed for toxicities with all immune agents included in this protocol including immune checkpoints and monoclonal antibodies)

Gastrointestinal irAEs		
Severity of Diarrhea / Colitis (NCI-CTCAE v4.03)	Management	Follow-up
Grade 1 Diarrhea: < 4 stools/day over Baseline Colitis: asymptomatic	Continue IO therapy/s Symptomatic treatment (for example, loperamide)	Close monitoring for worsening symptoms Educate subject to report worsening immediately If worsens: Treat as Grade 2 or 3/4

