5.4.8 Duration of Therapy

In the absence of treatment delays due to adverse events, treatment may continue until one of the following criteria applies:

1. Clinically significant progressive disease, or
2. Intercurrent illness that prevents further administration of either treatment agent, or
3. Patient request, or
4. General or specific changes in the patient's condition render the patient unacceptable for further treatment in the judgment of the investigator, or
5. Unacceptable toxicity that in the opinion of the investigator makes it unsafe to continue therapy.

It is planned that up to a total of 24 cycles of therapy will be administered for patients deriving benefit from this regimen. Continuation of therapy for patients completing 24 cycles of therapy may be considered on a case- by-case basis after discussion with the principal investigator and IND Office.

All patients receiving at least one dose of any of the two/three drugs to be received in the combination will be considered evaluable for toxicity and efficacy by intent-to-treat analysis.

5.5 Supportive Care:

Management Algorithms for Treatment of immuno-oncology agents Related

Adverse Events Immuno-oncology (I-O) agents are associated with AEs that can differ in severity and duration than AEs caused by other therapeutic classes. Avelumab and PF-04518600 are considered an immuno-oncology agent in this protocol. Early recognition and management of AEs associated with immuno-oncology agents may mitigate severe toxicity. These IO-agent/s has a known safety profile however, a general principle is that differential diagnoses should be diligently evaluated according to standard medical practice. Non- inflammatory etiologies should be considered and appropriately treated. Corticosteroids are a primary therapy for immuno-oncology drug-related adverse events, and avelumab is no exception. The oral equivalent of the recommended IV doses may be considered for ambulatory patients with low-grade toxicities. The lower bioavailability of oral corticosteroids should be taken into account when switching to the equivalent dose of oral corticosteroids. In cases with slightest suspicion of IO-toxicities it is encouraged that the treating physician consult the PI/Co-PI or immunotherapy expert in the department as soon as possible.

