11.0 STATISTICAL CONSIDERATIONS

This is an open-label Phase IB/II multi-arm study. The primary objectives are to determine the maximum tolerable dose (MTD) and identify the dose of PF-04518600 (Arm A), and to evaluate the composite complete response (CRc) within 3 months of therapy initiation of the combination therapies: Azacitidine + venetoclax + GO (arm B), Azacitidine + avelumab + GO (arm C), Azacitidine + venetoclax + avelumab (arm D), Azacitidine + avelumab + PF-04518600 (arm E), and GO + glasdegib (arm F), in patients with relapsed/refractory AML. A total of up to 87 patients will be enrolled in the study (arms with up to 24 patients per arm in arms C-D and 30 patients in arm B, in addition to the 4 patients enrolled in arm A and 5 patients enrolled in arm F at the time of closing these two arms).

Dose safety evaluation for Arm A (PF-04518600 alone in RR AML):

The 0.3 mg/kg dose of PF-04518600 will be evaluated as this was the dose selected to move forward from the solid tumor PF-04518600 single agent dose finding study (B0601002, ClinicalTrials.gov NCT02315066). Up to four patients will be enrolled at the dose level of 0.3mg/kg of PF-04518600. This arm will be closed at this time to further enrollment due to lack of clinical efficacy and competing options of higher priority at our institution.

Lead-in safety evaluation for Arm B-F

A lead-in safety evaluation for Arm B-F will be conducted to confirm the safety and tolerability of the treatment combination. Up to 30 patients in arm B, 24 patients in arms C-D and up to 21 patients in arms E-F will be enrolled. Enrollment must be halted while the first 6 patients in each treatment arm are evaluated for safety (i.e. after all patients have received 2 cycles of therapy, or been followed for at least 56 days from the start of treatment).

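### Table 12 bars study drug after any Grade 3 or 4 infusion reaction, but its footnote literally allows more avelumab after a second reaction of that severity

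*Combined protocol and SAP*

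**What the plan says.** Section 6.2 covers the two IO agents, avelumab and PF-04518600. Table 12 sets the action by grade. At Grade 1 the rate is halved. At Grade 2 the infusion stops and restarts at half the rate once the reaction has settled to Grade 1 or better. At Grade 3 or 4: "Subjects have to be withdrawn immediately from study drug treatment and must not receive any further study drug treatment". That row makes no distinction between a first and a later reaction. Its definition of Grade 3 includes "recurrence of symptoms following initial improvement".

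The footnotes add that a rate once reduced stays reduced. They then deal with a "second infusion-related reaction Grade ≥ 2 on the slower infusion rate": the infusion is stopped and the patient is to be "removed from study treatment unless the patient is deriving clinical benefit in which the agent may be continued after discussion with the PI", with the risk/benefit discussion documented.

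Section 5.4.4 gives the general rule for these agents: "Any Grade 4 drug-related AEs require treatment discontinuation with IO-agent/s", apart from certain isolated laboratory values. Grade 3 drug-related events also end the agent, with a short list of exceptions. The section then says: "Infusion-related reactions, hypersensitivity reactions (Grades 1 to 4), and tumor lysis syndrome should be handled according to guidelines provided".

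On exposure, section 5.4.8 states: "It is planned that up to a total of 24 cycles of therapy will be administered for patients deriving benefit from this regimen". Section 11.0 plans "up to 24 patients per arm in arms C-D and 30 patients in arm B".

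**The concern.** The Grade 3/4 row and the footnote give opposite answers for the same patient. The footnote sets a floor of Grade 2 with no ceiling, so a second reaction of Grade 3 or 4 triggers it, and with it the clinical-benefit exception. Nothing in section 6.2 says that the row overrides the footnote.

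The stake is patient safety. Section 2.3.2 lists infusion and hypersensitivity reactions among the main identified risks of avelumab. Section 4.2.1 excludes anyone known to have had a Grade 3 or worse hypersensitivity reaction to a monoclonal antibody. Read literally, the footnote lets an enrolled patient be given avelumab again after an on-study reaction of the same severity, on the strength of a conversation with the PI and a chart entry. By comparison, section 5.6 asks for approval by both the PI and the medical monitor to continue an essential prohibited medication.

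**Working it through.** No formula applies to the conflict itself, so the check sets the rules side by side.

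**Step 1: does the slower-rate condition narrow the footnote?** In practice it does not. A first reaction of Grade 1 or 2 halves the rate, and the footnote keeps it reduced for every later infusion. Any second reaction after a Grade 1 or 2 reaction is therefore on the slower rate.

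**Step 2: go through the sequences.**

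| First reaction | Second reaction | Table 12 row | Footnote | Result |
|---|---|---|---|---|
| Grade 3 or 4 | None possible | Drug ended | Not reached | Consistent |
| Grade 1 or 2 | Grade 1 | Slow the infusion | Not triggered | Consistent |
| Grade 1 or 2 | Grade 2 | Pause, then resume slower | Remove, unless benefiting | No clash with the Grade 3/4 bar |
| Grade 1 or 2 | Grade 3 or 4 | Drug ended, no exception | May continue if benefiting | **Conflict** |

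Only the last sequence is in conflict.

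**Step 3: can that sequence arise other than by sudden escalation?** Possibly. Because the Grade 3 definition includes symptoms that come back after improving, a patient paused for a Grade 2 reaction whose symptoms return when the infusion restarts at half rate can be graded 3. If that return is counted as a second reaction, it meets both the row and the footnote. The documents do not say how to count it. The conflict in Step 2 does not depend on this.

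**Step 4: does another section decide?** Section 5.4.4 points the same way as the row, but it then hands infusion reactions of all grades to the guidelines provided, which leads back to Table 12 with both the row and the footnote. The introduction to section 6.2 lets the guidance be adapted to institutional standards, but it does not rank the two rules.

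**Step 5: size of the group.** Arms A, E and F are closed (section 3.1, Table 1). Of the open arms, B has 30 patients and receives no avelumab; C and D have 24 each and receive it as their only IO agent.

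- Patients under the rule: 24 + 24 = 48.
- Planned in the open arms: 30 + 24 + 24 = 78.
- Share: 48 / 78 = 61.5%.
- Maximum avelumab infusions per patient: 2 per cycle (Days 1 and 14, section 5.2) × 24 cycles = 48.

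These figures bound exposure to the rule. They are not an estimate of how many patients would be affected.

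**Step 6: effect on the statistics.** Under section 3.4, clinically significant Grade 3 or 4 non-hematologic events in the first cycle count as DLTs by grade. Whether the drug is later continued does not alter that count, so the monitoring boundaries and operating characteristics in section 11.0 are unchanged.

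**The case against.** The best reply is that the two rules differ in force and can be read together. The row is a flat prohibition, while the footnote only permits. A clinician who withdraws the patient complies with both, and an optional allowance does not obviously lift a ban. On this reading the row ends treatment at Grade 3 or 4, and the footnote does its own work at a second Grade 2 reaction, which the Grade 2 row would otherwise allow to resume. Section 5.4.4 supports this as the intent: it has an almost identical benefit exception, expressly tied to a repeat of the same Grade 2 event, and it offers no benefit exception at Grade 3 or 4.

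This is a plausible account of what was meant, but it is not what the footnote says. The footnote is also the more specific rule for second reactions, and the protocol does accept continuation for benefit after serious toxicity elsewhere: section 5.2 lets Arm A patients continue after a DLT following discussion with the PI. The parallel in section 5.4.4 is best seen as support for the edit.

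Other points on that side:

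- **Reporting.** Grade 3 or 4 infusion reactions go to the company's medical monitor within 5 days (section 6.2), and SAEs go to the IND Office and the company (sections 10.3 and 10.5). The event would be seen, but none of these steps is an approval to redose.
- **Recurrence of symptoms.** This wording may simply describe one reaction that worsens to Grade 3, in which case the row applies and the footnote is not reached. That is fair, and the point is therefore conditional.
- **Rarity.** An affected patient needs an earlier mild or moderate reaction, a later severe one, evidence of benefit, and a PI willing to continue. Premedication is mandatory. This stands, and it is why no event count is claimed.

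**Conclusion.** The concern holds. For one sequence, a Grade 1 or 2 reaction followed by a Grade 3 or 4 reaction on the slower rate, Table 12 both forbids and allows further IO agent, and no other section resolves it. The exception becomes usable once benefit can be judged, so it applies to the patients planned for the longest exposure.

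The group governed by the rule is up to 48 of 78 patients in the open arms. This uses the arm sizes in Table 1 and section 11.0, and the ceiling of 48 infusions assumes all 24 planned cycles are given. How often the sequence would occur cannot be worked out from the documents.

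This is a safety instruction that should be corrected. It does not affect sample size, DLT counting for clinically significant Grade 3 or 4 reactions, or the stopping rules.

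**What to change.** In the Table 12 footnote on second reactions, replace Grade ≥ 2 with Grade 2, and add one sentence:

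> Any Grade 3 or 4 infusion-related reaction, first or later, permanently ends the IO agent.

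Returning symptoms that are graded 3 then fall under the row however they are counted, and the benefit exception is kept for a second Grade 2 reaction only. This also brings the footnote into line with the Grade 2 exception in section 5.4.4.

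The cost is one changed grade and one added sentence. There are no new procedures and no change to sample size or monitoring. What is given up is the discretion to continue a benefiting patient after a second Grade 3 or 4 reaction, which the row already denies.
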